Methods and Analysis: This will be a single center prospective before-and-after proof-of-concept study. Adults (18 years and older) undergoing elective surgery and recovering in two selected PACU bays will be enrolled. During the initial 3-month observation phase, clinicians in the telemedicine center will not communicate with clinicians in the PACU, unless there is a specific patient safety concern. During the subsequent 3-month interaction phase, clinicians in the telemedicine center will provide structured decision support to PACU clinicians. The primary outcome will be time to PACU discharge readiness determination in the two study phases. The attitudes of key stakeholders towards the telemedicine center will be assessed. Other outcomes will include detection of physiological derangements, complications, adverse symptoms requiring treatments, and emergencies requiring medical intervention.

Registration Information: This trial is registered on clinicaltrials.gov, NCT04020887

Keywords:

Telemedicine, Post-Anesthesia Care Unit, Protocol, Proof-of-Concept, Observational Study

Introduction

After invasive procedures in the operating room (OR) or other procedure rooms, patients are usually transferred to a post-anesthesia care unit (PACU) for high acuity monitoring. The PACU period is important for patients, especially since they often are still in a vulnerable state.^{1,2} Patients are prone to peri-procedural and post-anesthetic complications including dehydration, anemia, coagulopathy, bleeding, hypothermia, delirium, respiratory depression, airway obstruction, bronchospasm, hypotension, kidney injury, arrhythmias, metabolic acidosis, hypoxemia, glucose and electrolyte abnormalities, atelectasis, and pulmonary edema.^{3,4} These complications must be recognized and appropriately managed by PACU clinicians. Furthermore, PACU clinicians need to identify and manage patients' adverse symptoms including pain, nausea, urine retention, weakness, and itching, which are common after invasive procedures, whether with or without general anesthesia.

The ideal PACU environment provides close monitoring and prompt rescue for peri-procedural complications, while also efficiently transferring patients to their next phase of care. For example, when patients deteriorate in the PACU, it is important to recognize this early, intervene appropriately, and arrange transfer to a higher acuity area, such as an intensive care unit, when warranted.

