This proof-of-concept study has been reviewed and granted a waiver of informed consent for all subjects enrolled by the Human Research Protection Office at Washington University in St. Louis (HRPO#201901180) and is registered at clinicaltrials.gov (NCT04020887). It is infeasible to conduct this proof-of-concept study without a waiver of consent. Additionally, this study has been determined to involve no more than minimal risk to participants, as study participation would not deviate from or delay current standards of peri-anesthesia care. Both the “Good ReseArch for Comparative Effectiveness” (GRACE) checklist⁷ and PICOTS framework⁸ (Table 1) were used in designing this study.

The conduct and reporting of this observational study will follow the “Reporting of studies Conducted using Observational Routinely-collected health Data” (RECORD)⁹ statement and the “Strengthening the Reporting of Observational Studies in Epidemiology” (STROBE)¹⁰ statement guidelines for reporting observational studies.

[figure not shown]
Table 1. PICOTS Framework

PICOTS typology for a comparative effectiveness research protocol	
Population	Adult (18 years and older) patients undergoing elective surgery
Intervention	Telemedicine center for PACU
Comparator	Current post-anesthesia care unit practice
Outcomes	(i) potential utility, and (ii) acceptability of integrating telemedicine in the post-anesthesia care unit environment
Timing	6-month study duration

Setting	Hospital environment – Barnes-Jewish Hospital, St. Louis, Missouri
---------	--

Primary Intervention: Telemedicine Center for PACU

Two bays in Barnes Jewish Hospital (BJH) in St. Louis, Missouri, will be equipped for telemedicine interaction (Figure 1). Video cameras and monitors have been installed in each of these bays to allow for remote monitoring, as well as two-way video communication during the interaction phase. The telemedicine center is staffed by attending anesthesiologists along with certified registered nurse anesthetists (CRNAs), anesthesiology residents, and student registered nurse anesthetists (SRNAs), and is currently providing evidence-based support to clinicians in the operating rooms.^{11–14}

Two PACU bays located across from nurse's station

High-resolution camera for patient monitoring and communication

Ultra-sharp monitor on telescoping arm for two-way patient communication

High-definition microphone for patient monitoring and communication

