We will conduct focus groups with stakeholders to gain insights regarding their perceptions of barriers and facilitators related to the above-noted PACU functions before and after the implementation and use of a telemedicine center for the PACU. We will also gather perspectives from the stakeholders on the role and impact of the telemedicine center on their individual and team workflows in the PACU and between units during care transitions. Focus group participants will include nurses, anesthesiologists, surgeons, hospital administrators, and PACU telemedicine center clinicians. Our focus groups will be homogeneous in order to understand the clinician workflow based on their professional role, and their use of the telemedicine center in supporting their role and responsibilities. Each focus group will comprise five to six participants. This will allow in-depth discussions of the workflow problems and unintended

consequences caused by the implementation and use of the telemedicine center for the PACU. The focus group sessions will be guided by a semi-structured interview guide focused on the following themes: (1) PACU core functions, (2) PACU patient workflow, (3) PACU clinician activities and tasks, (4) tools and technologies used to support the PACU workflow, (5) major barriers to PACU functions, (6) use of a telemedicine intervention as a potential mechanism to support effective and efficient functioning of the PACU. We plan to conduct 6-8 focus group sessions (4 pre-intervention during observation phase, and 4 post-intervention during interaction phase) or until data saturation is attained.

Study Size

Patients are allocated to PACU bays according to the discretion of the nurse in charge of the PACU. Currently, approximately two patients per day are cared for in each bay in the participating PACU. Therefore, the telemedicine team will monitor approximately four patients per day over the course of the proof-of-concept study. We estimate that 500 patients will be included in this proof-of-concept study (250 per monitored phase) (Figure 4).

[figure not shown]

Figure 4. Allocation of sample size and PACU layout for proof-of-concept study

Statistical Methods

Primary Outcome

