This is a proof-of-concept study and will only address surrogate outcomes. The primary outcome (time to PACU discharge readiness) will use two comparison groups. First, historical controls will be drawn from the observation phase. A propensity score for inclusion into the study will be generated as a function of (minimally) surgery performed, day of week, time of day, age, and sex. 3:1 matched control patients will be included. The outcome will be analyzed with interrupted time series methods with flexible functions of calendar time used to adjust for secular trends; the study hypothesis is a non-zero discontinuity at telemedicine implementation.

That is, if Y_i is the outcome for the i th patient at time t_i with covariate vector X_i , while the implementation time is t_0 , and $I()$ is the indicator function,

$$Y_i = f_1(t_i)I(t_i < t_0) + f_2(t_i)I(t_i \geq t_0) + X_i\beta + \epsilon H_0: f_1(t_0) = f_2(t_0)$$

where f_1 and f_2 are smooth functions. Other patient factors known to strongly influence PACU length of stay (age, ASA physical status, number of co-morbidities, morbid obesity, obstructive sleep apnea, surgical specialty, primary anesthesia type, history of postoperative nausea and vomiting, preoperative pain, and scheduled case duration) will be included as covariates. The minimization criteria will be least squares or trimmed least squares or other robust criteria if there are substantial outliers. Outcomes will be examined for residual auto-correlation, and if non-negligible, auto-correlation robust standard errors (such as Newey-West errors) and an ARIMA model will be reported. Confidence intervals will be generated by non-parametric bootstrap sampling where possible. No adjustment will be made for matching, but bootstrap methods will respect the matched “units.” P-values will be generated both by likelihood ratio tests and by using non-deployment times as a null distribution; that is, we will run the same analysis looking for discontinuity at times remote from the true implementation time. We will conduct sensitivity analyses with transformations of the outcome variable. We will use an excluded run-in period of 1 month as a sensitivity analysis. Because hospital length of stay is unlikely to be meaningfully affected by a telemedicine center for the PACU, but does track overall acuity and surgical severity, we will use hospital length of stay as a control time series.

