Contemporaneous control patients will also be gathered. A propensity score for study inclusion will be generated as a function of (minimally) surgery performed, calendar time, time of day, age, and sex. 3:1 matched control patients will be included. Differences will be analyzed by t-tests using permutation calibration. Confidence intervals on the difference in mean time to discharge readiness will be generated by nonparametric bootstrap. We will include a sensitivity

analysis where the interrupted time series method includes historical and contemporaneous control patients with the treatment indicator T for study patients,

$$Y_i = f_1(t_i)I(t_i < t_0) + f_2(t_i)I(t_i \geq t_0) + X_i\beta + T_i + \epsilon.$$

Based on data from our EHR, patients are currently in PACU for a mean of 150 min (standard deviation = 65 min) before they are determined to be suitable for discharge. Based on these values, with 250 patients in each phase (observation and interaction), this observational before and after study will have >70% power with an alpha <0.005 and > 90% power with an alpha <0.05 to detect a mean decrease in 20 min (from 150 min to 130 min) to PACU discharge readiness time. Statistical testing will be with appropriate statistical software. Using non-parametric bootstrap of historical data and a 3:1 control sampling ratio, the average standard error on the difference in means under the null hypothesis was 5.5 minutes, giving an anticipated 95% confidence interval width of 22 minutes. A somewhat larger standard error will be encountered when adjusting for covariates or secular trends; however, this suggests that we will be able to resolve differences in PACU readiness times of 20-25 minutes. This difference of approximately a third a standard deviation is usually regarded as a “small-moderate” sized effect.

Secondary Outcomes

Hand-off quality assessment from the PACU nurse binary survey response will be analyzed using a logistic regression model adjusting for surgical service, age, and sex. Because observation resources are required for hand-off evaluations, no matching will be performed, and no contemporaneous controls will be gathered. Adjusted differences in rates of inadequate hand-off will be summarized with 95% confidence intervals and model-based p-values.

Observed reported hand-off communication quality will be presented as a purely descriptive result.

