Multiple sources will be utilized for data collection from which outcome measures will be extracted. Data from AlertWatch will be automatically logged to a secure database. Preoperative patient characteristics, comorbidities, surgical and clinical history, as well as perianesthesia information will be captured using Epic Systems software (Verona, WI, USA). Prospective data will be collected from Epic Systems for the datapoints mentioned throughout the proof-of-concept study.

Relevant PACU information outlined in Tables 2-5 for patients in this study will be collected and entered into a REDCap database managed by Washington University. Data will not be shared with others outside the research team.

Methodological strengths and limitations

A strength of this study is its pragmatic approach as a real-world study with measurable aims. Feasibility will be determined, and information will be provided regarding logistical implications of establishing a telemedicine solution for the PACU. Many telemedicine solutions have been implemented without considering barriers and facilitators, such as cultural and political obstacles. This study proactively addresses these concerns, which might facilitate future successful implementation and generalization of similar telemedicine initiatives. Specific

functions of the PACU have been detailed, and the methods of this study will allow assessment of the ability of the telemedicine center to facilitate the accomplishment of these functions. This study also has important limitations. First, as a proof-of-concept, it will only include two PACU bays. Thus, its applicability to a large PACU will not be resolved. Second, PACU clinicians will be aware of the initiative, which could modify their behavior during the conduct of the study. Third, as the study design is observational with a before and after approach, improvements (for example in time to discharge) cannot be causally attributed to the intervention; there could be confounding explanations. Fourth, the current discharge criteria for the PACU do not have a firm evidential foundation (there is no gold standard measure for discharge readiness), and clinician gestalt plays an important role. This limitation can be addressed through development of rigorous, reliable and practical criteria. Finally, as a single center study, results will not necessarily be broadly generalizable.

Adverse Events and Safety Monitoring

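### Entry depends on unblinded, discretionary bay placement, and no named adjustment variable records the actual intraoperative course or condition on PACU arrival, so a placement change at the switch could mimic or mask a telemedicine effect.

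*Combined protocol and SAP*

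**What the plan says.** The abstract's Methods and Analysis paragraph sets the entry condition: "Adults (18 years and older) undergoing elective surgery and recovering in two selected PACU bays will be enrolled". Study Size says how the bays are filled: "Patients are allocated to PACU bays according to the discretion of the nurse in charge of the PACU". No placement rule, placement log or comparison of bay case mix by phase is planned.

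Staff are not blinded. Methodological strengths and limitations accepts that "PACU clinicians will be aware of the initiative, which could modify their behavior during the conduct of the study".

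Under Statistical Methods, Primary Outcome, the hypothesis is a jump in time to discharge readiness at implementation, estimated by interrupted time series. The adjustment consists of:

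- a propensity score for inclusion with historical controls, "as a function of (minimally) surgery performed, day of week, time of day, age, and sex";
- a propensity score with contemporaneous controls, "as a function of (minimally) surgery performed, calendar time, time of day, age, and sex";
- a covariate vector X holding baseline patient factors, surgical specialty and anesthesia type, and ending with "history of postoperative nausea and vomiting, preoperative pain, and scheduled case duration".

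The same section adds placebo implementation dates, a sensitivity analysis that drops a one-month run-in, and hospital length of stay as a control series, chosen because it follows acuity and surgical severity.

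**The concern.** A charge nurse choosing a bay can act on how the operation went and how the patient looks on arrival. Neither is among the named adjustment variables. Operative duration, the nearest candidate, enters only as scheduled.

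The bays also change character at the switch. In the observation phase the telemedicine center stays silent unless there is a safety event. In the interaction phase it talks to patients and staff and works with them as one team. That is a plausible reason for the nurse to place different patients there.

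If placement did change at the switch and stayed changed, the part not explained by X would go into the same term as the treatment effect. Quicker patients would produce a false benefit, and slower patients would hide a real one. The contemporaneous comparison is exposed too, because it sets patients placed in the bays against patients who were not. The bays' position ("Two PACU bays located across from" the nurse's station, per Figure 1) is the same in both phases. It cannot by itself cause a jump, but if it influences placement it could separate bay patients from controls in other bays.

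**Working it through.** **1. The plan's own figures.** Inputs from Statistical Methods, Primary Outcome: SD 65 min, 250 patients per phase, target decrease 20 min.

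- SE of the difference = 65 × √(2/250) = 5.81 min; 20/5.81 = 3.44.
- Two-sided alpha 0.05: Φ(3.44 − 1.96) = 93.1% (plan: above 90%).
- Two-sided alpha 0.005: Φ(3.44 − 2.81) = 73.7% (plan: above 70%).
- Confidence interval width from the bootstrap SE of 5.5 min: 2 × 1.96 × 5.5 = 21.6 min (plan: 22).

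The sample-size arithmetic is sound and is not at issue.

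**2. Where a placement shift goes.** The model compares f₁(t₀) with f₂(t₀). A lasting shift of b minutes in unmeasured prognosis, starting at t₀, adds b to f₂(t₀) − f₁(t₀). A shift that built up slowly would be partly absorbed by the smooth functions. The planned safeguards bear on an abrupt shift as follows:

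- *Placebo dates* test for jumps elsewhere, not for selection at the true date.
- *Dropping the run-in month* does not remove a shift that lasts.
- *The sensitivity model with T* has one term for study patients, constant across phases, so it cannot represent a change in selection at the switch.
- *The contemporaneous t-test* relies on matching on at least five variables. X is not specified for it.
- *Hospital length of stay* can signal a shift in acuity but has no decision rule and does not adjust the estimate.

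**3. Size, on an assumed shift.** The documents give no value for b. Assume 0.05, 0.1 or 0.2 SD, that is 3.25, 6.5 or 13 min. With no telemedicine effect, the rejection rate at two-sided 5% is 1 − Φ(1.96 − b/5.81) + Φ(−1.96 − b/5.81). With a true 20-min decrease and slower patients placed in the bays, power falls to Φ((20 − b)/5.81 − 1.96).

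| Assumed shift b | Share of 20-min target | False-positive rate | Power if the shift masks |
|---|---|---|---|
| 3.25 min | 16% | 8.6% | 82% |
| 6.5 min | 33% | 20.1% | 64% |
| 13 min | 65% | 60.9% | 23% |

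These rates belong to an unadjusted comparison of 250 with 250. The planned discontinuity test would have a larger SE, hence lower false-positive rates, but the same bias in minutes.

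**4. How well length of stay would detect a shift.** Let a shift of b minutes move length of stay by r × b/65 of its SD (r is an assumption). Detection probability with 250 per phase is about Φ(r × (b/65)/√(2/250) − 1.96). For b = 10 min it is 6%, 14% and 41% at r = 0.25, 0.5 and 1. For b = 20 min it is 14%, 41% and 93%.

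**The case against.** The strongest reply is that the plan already treats bay placement as the thing to be modeled. Both propensity scores are for study inclusion, which is recovery in a study bay. Both variable lists are stated as minimums, and Data Collection says that perianesthesia information will be captured. The length-of-stay series is a deliberate acuity check. The limitations section says that improvements cannot be attributed causally to the intervention. The motive for steering is also modest: telemedicine clinicians write no orders and give opinions only, and the bays are already watched during the observation phase.

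Much of this stands, and it rules out three stronger readings:

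- *That every adjustment variable is preoperative or scheduled.* The procedure variable is the surgery performed, and anesthesia type and time of day are not said to be planned values.
- *That a shift would necessarily be reported as a telemedicine effect.* The causal disclaimer and the length-of-stay series argue against that.
- *That the nurse will steer patients.* Nothing in the documents shows it. If sicker patients were steered to the bays, the hypothesized decrease would be masked, not imitated.

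What the reply does not supply is a commitment. A minimum list permits intraoperative variables but names none, and X carries no such qualifier. A general disclaimer does not identify this entry route, and length of stay is a weak signal for moderate shifts.

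**Conclusion.** The point holds as a gap in the named adjustment set, not as a demonstrated bias. Three facts are in the text: placement decides entry, the person placing patients is unblinded, and no named variable measures the actual intraoperative course or arrival condition. It follows that an abrupt and lasting change in placement at the switch would enter the primary estimate, in either direction, and that nothing planned can remove the part left unmeasured.

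The size is unknown. As an illustration, an assumed residual shift of 6.5 min is about a third of the target effect and takes the false-positive rate to about 20% on the unadjusted scale. This rests on SD 65 min, 250 per phase, a normal approximation and an assumed shift. For a proof-of-concept study that disclaims causal attribution, this is a worthwhile and cheap improvement, not a flaw that invalidates the design.

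**What to change.** In Statistical Methods, Primary Outcome:

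1. Add actual case or anesthesia duration, and any other intraoperative variables fixed before PACU arrival and available in the perianesthesia data, to both propensity scores and to X, in the main and sensitivity models.
2. Report the case mix of the study bays against non-study bays, by phase.
3. Use first PACU vital signs only in a sensitivity analysis. Under Hand-off Activity, telemedicine joins the OR-to-PACU hand-off in the interaction phase and shares information that could inform treatment, so these values may already reflect the intervention.

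Leave bay assignment unchanged. A fixed placement rule may look attractive, but the consent waiver rests on no departure from current care, and a rule with open clinical override would keep the selection it was meant to remove.

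The cost is a few extra EHR fields, for controls as well as study patients, and a small amount of analysis. These variables will narrow the gap but not close it, because arrival condition stays outside the main adjustment.

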Severe pain (Numerical Rating Scale >7/10)	Itching
Chest pain unrelated to surgery	

Table 4. Emergency medical interventions

Did the telemedicine center contact PACU clinicians for any of the following interventions:	
Intubation	Unplanned transfusion
Assisted ventilation	Naloxone administration
Cardiopulmonary resuscitation	Return to OR
Cardioversion	Other (free text box)
If Yes, please check all that apply:	
 PACU nurse already aware of the situation	
 PACU nurse unaware of the situation	
 PACU nurse disagreed with the assessment	
 PACU nurse had already spoken to the supervising physician regarding the situation	

Other (please describe):

*Only the telemedicine center will document the detection of urgent situations.

Table 5. Patient discharge readiness

At what time did the patient sufficiently recover to be discharged (case attending anesthesiologist contacted for discharge)?	
PACU Nurses	Telemedicine Center for PACU
Time anesthesiologist is contacted for discharge evaluation	Time ready for discharge
Aldrete Score at discharge	Aldrete Score at discharge
	Unable to determine patient's readiness for discharge
Modified Aldrete Scale Component and Scoring Parameters	If Unable to fully assess, select reason(s) why (Checkbox)
Respiration	 More patient information needed  Equipment issues  Patient cooperation  Other (free text box)
2 – Able to take deep breath and cough	
1 – Dyspnea / Shallow Breathing	
0 – Apnea	
O₂ Saturation	
2 – Maintains > 92% on room air	
1 – Needs O ₂ inhalation to maintain O ₂ saturation > 90%	
0 – Saturation <90% even with supplemental O ₂	
Consciousness	
2 – Fully awake	
1 – Arousable on calling	
0 – Not responding	
Circulation	
2 – BP ± 20mmHg pre-op	
1 – BP ± 20-50mmHg pre-op	
0 – BP ± greater than 50mmHg pre-op	
Motor Activity	
2 – Able to move 4 extremities voluntarily or on command	
1 – Able to move 2 extremities voluntarily or on command	
0 – Able to move 0 extremities voluntarily or on command	

Interaction Phase (3 months)

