In the three months following the observation phase, clinicians in the telemedicine center will interact with patients and clinicians associated with the designated PACU bays using audio-visual technology. PACU clinicians and clinicians in the telemedicine center will become a “fused” team, and the telemedicine center will continue to document information on physiological derangements (Table 2), treatable symptoms (Table 3), situations requiring urgent medical intervention (Table 4), and discharge readiness (Table 5).

The telemedicine center clinicians will assess patients’ discharge readiness throughout their PACU stay. A modified Aldrete scale along with clinical judgment will guide the telemedicine center clinicians in determining readiness for discharge (Table 5). After discharge readiness has been determined by the telemedicine center, the attending anesthesiologist in the telemedicine center will document discharge readiness in AlertWatch and REDCap, and contact the relevant anesthesiologist. The telemedicine center for PACU will document when this information was communicated. At any point clinicians in the telemedicine center might decide to contact PACU clinicians (nurse or physician) if they have specific concerns regarding patients. If the telemedicine center clinicians feel that they cannot adequately assess a patient’s clinical status, they will notify the PACU clinicians. This will be documented together with a relevant explanation (Table 5).

Final determination and sign-off regarding discharge suitability will be made by the anesthesiologist in the PACU. With this proof-of-concept research project, there will be no change in relation to which clinicians have responsibility for decision making and clinical care. The telemedicine center clinicians will not write any orders in the medical record, and will provide opinions only to physicians and nurses who are responsible for patient care in the

PACU. The responsibility to call for help when patients are deteriorating will remain with the PACU nurses, as is the current standard in that environment. The notion is that the telemedicine center will not lead to any decrement in the care that PACU patients are currently receiving from nurses and physicians in that environment.

The successful integration of the telemedicine center into each of the core PACU functions will be measured in the following ways:

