Physiological derangements – Success will be measured (in the observation phase) by the ability of the telemedicine center clinicians to identify physiological derangements as they are occurring in the PACU. The extent to which the telemedicine center clinicians can identify these physiological derangements will be measured by comparing PACU nurse and telemedicine center assessment surveys for each patient (Figure 3).

Symptom identification and management – Success will be measured (in the observation phase) by the ability of the telemedicine center clinicians to identify treatable symptoms as they arise in the PACU. The extent to which the telemedicine center clinicians can identify these treatable symptoms will be measured by comparing PACU nurse and telemedicine center assessment surveys for each patient (Figure 3).

Emergency situations – Success will be measured (in the observation phase) by the ability of the telemedicine center clinicians to identify situations requiring emergency medical intervention as they are occurring in the PACU. By construction, any time the telemedicine center feels that an emergency situation is present, preserving patient safety mandates contacting the bedside clinician.

During each such contact, the telemedicine center clinician will ask if the PACU nurse was already aware of the situation, disagreed with the assessment, and had already spoken to the supervising physician regarding it. The occurrence of emergency medical situations will be extracted from the electronic health record, and the agreement between telemedicine center and PACU nurse assessments will be quantitated.

PACU discharge – Success will be measured by the ability of the telemedicine center clinicians to identify when patients are ready for discharge (observation phase [without communication] and interaction phase [active communication with patient and PACU clinicians]) (Figure 3). The impact of the telemedicine center on this key function will be examined based on feedback from key stakeholder focus groups (interaction phase; see *Aim 2*). The difference between sign-out times in the observation and the interaction phases will be compared.

Data collection methods and measures during the interaction phase

Aim 1: Demonstrate the potential utility of a telemedicine center for the PACU, to assist with PACU functions

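### Is the primary outcome, time to PACU discharge readiness, too loosely defined for the planned comparisons to be run on it?

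*Combined protocol and SAP*

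**What the plan says.** The abstract states "The primary outcome will be time to PACU discharge readiness determination in the two study phases". The Primary Outcome section uses a shorter label, "The primary outcome (time to PACU discharge readiness) will use two comparison groups", and goes on to 3:1 matched historical controls analysed by interrupted time series and 3:1 matched contemporaneous controls analysed by permutation-calibrated t-tests.

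Further down, the same section gives the planning values: by the hospital's EHR, a mean of 150 minutes (SD 65) in the PACU before patients are judged suitable for discharge. It also gives a standard error of 5.5 minutes from a bootstrap of historical data with 3:1 control sampling.

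Other times appear elsewhere. Table 5 has a nurse column, "Time anesthesiologist is contacted for discharge evaluation", and a telemedicine column for the time the patient is ready. The Interaction Phase section has the telemedicine attending "document discharge readiness in AlertWatch and REDCap, and contact the relevant anesthesiologist", and then says "Final determination and sign-off regarding discharge suitability will be made by the anesthesiologist in the PACU". The success measure for PACU discharge adds "The difference between sign-out times in the observation and the interaction phases will be compared". Under Secondary Outcomes, the mean difference in ready-for-discharge times is tested against zero.

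**The concern.** Readiness, readiness determination and sign-out are three labels, and the plan never says which recorded event is the outcome. The two Table 5 columns capture different events from different recorders, and the Secondary Outcomes section expects the telemedicine team to find patients ready before the bedside nurse does.

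Neither column would make a good primary outcome:
- The telemedicine time comes from the intervention team itself, under different conditions in the two phases: "observation phase [without communication] and interaction phase [active communication with patient and PACU clinicians".
- The contact time could shift in meaning once telemedicine also calls the anesthesiologist.
- Neither column is described for matched controls.

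If one group were timed by one recorder and its comparator by another, the average gap between recorders would look like a treatment effect. The limitations section concedes that readiness has no gold standard, so no outside convention settles the event.

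**Working it through.** **1. The plan's own figures.** Inputs from the Primary Outcome section: 250 per phase, SD 65, difference 20 minutes.
- SE = 65 × √(2/250) = 5.81.
- Two-sided power at alpha 0.05: Φ(20/5.81 − 1.96) = 93.1%, against a stated figure above 90%.
- At alpha 0.005: Φ(20/5.81 − 2.81) = 73.7%, against a stated figure above 70%.
- Interval width from the bootstrap SE: 2 × 1.96 × 5.5 = 21.6, stated as 22.

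All reproduce, so the arithmetic is not in question.

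**2. The candidate times side by side.**

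| Time | Where | Monitored patients, both phases? | Matched controls? |
|---|---|---|---|
| Telemedicine judgment of readiness | Observation and Interaction Phase sections; Table 5 | Yes, unless marked as undeterminable | Not described |
| Nurse-column contact time | Table 5 | Form described for the observation phase; continuation not stated | Not described |
| Telemedicine communication of readiness | Interaction Phase section | Interaction phase only | No |
| Anesthesiologist's sign-off or sign-out | Interaction Phase section; success measures | Yes | A step of usual care, so it should occur for them |
| EHR time behind the 150-minute mean | Primary Outcome section | Yes, if still recorded | Already extracted for past patients |

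The last two rows may be the same event. Only they can serve every planned comparison.

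**3. What the matching requires.** Three controls for each of 250 study patients is 3 × 250 = 750. The monitored observation phase supplies about 250. If controls are not reused, at least 750 − 250 = 500 must come from patients the telemedicine center did not monitor. The Data Collection section describes the Tables 2–5 data only for study patients. The outcome therefore has to come from routine records.

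**4. What the bootstrap shows.** With SD 65, the formula SE for 250 against 750 is 65 × √(1/250 + 1/750) = 4.75. The stated 5.5 is larger (implied SD 5.5 / √(1/250 + 1/750) = 75.3), so it did not come from putting 65 into that formula. This is consistent with resampling patient-level times. An outcome value for non-study patients was therefore in hand at planning.

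**5. What a recorder gap would do.** The documents give no gap size, so the values here are assumptions. With no true effect and a gap d, the chance of a significant result is Φ(d/SE − 1.96) + Φ(−d/SE − 1.96).
- 250 against 250, SE 5.81: d = 5, 10, 15 minutes gives 14%, 41%, 73%.
- Time series with linear trends each side and patients spread evenly over time, SE = 65 × √(4/250 + 4/250) = 11.63: 7%, 14%, 25%, and only if every record after implementation differs from every record before it.
- d = 0, one time for everyone: the nominal 5% in each case.

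The first two lines need compared groups to be timed by different recorders. No section says that they are.

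**The case for a change.** The strongest reply is that the EHR is named as the source of planning values, not of the trial endpoint, and that the EHR event itself is not identified. Table 5 is also where study staff write a readiness time down, under the question "At what time did the patient sufficiently recover to be discharged (case attending anesthesiologist contacted for discharge", so a reader could take it for the primary outcome. With a stated hypothesis test and power, proof-of-concept status does not excuse leaving the event open, and in principle it could be picked after the data are seen. The difference between the bootstrap SE of 5.5 and the 4.75 implied by SD 65 might even hint that two data extracts were used.

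Part of this stands. The definition has to be assembled from several sections, the labels are not reconciled, and sign-off, if that is the event, includes the anesthesiologist's response time as well as patient recovery.

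The rest does not carry. No section makes a Table 5 time the primary outcome, and those times suit the secondary agreement analysis. The contact entry is worded in the passive, so an earlier contact prompted by telemedicine may simply be the intervention working. The SE difference need not reflect a different event, because a bootstrap need not reproduce SD 65. Later selection of the event is possible in principle, but a time had already been extracted to produce the mean, SD and bootstrap SE, which leaves less room for it.

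**Conclusion.** No change to the plan follows. The outcome is under-described but recoverable: time in the PACU until the patient is determined suitable for discharge, taken from the EHR, most likely at the anesthesiologist's sign-off. The matched-control design and the historical bootstrap both need a time that exists for non-study patients, which rules out the Table 5 times as the common outcome. Applied identically to study patients in both phases and to all controls, one EHR time gives a recorder gap of zero and leaves the error rate at its nominal level. Recording which field was used is routine documentation when the data are extracted. It replaces no stated method and alters neither the models nor the 250 per phase.

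This rests on two assumptions that the documents support but do not state: that the EHR event behind the 150-minute figure is the one analysed, and that it is timestamped in the same way for controls. If the analysis instead mixed recorders across compared groups, the figures in step 5 would apply. Nothing in the plan indicates that it will.
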